#### 3. Analysis Population

The statistical analysis sets involved in this study are as follows:

**Enrolled Population:** including all subjects who sign informed consent form and are successfully screened.

**Safety Analysis Set:** including all the subjects who received at least one dose of the study drug. This analysis set will be used for analysis of safety endpoint.

Efficacy Analysis Set: including all the subjects who received at least one dose of the study drug and have undergone at least one post-baseline efficacy assessment. This analysis set will be used for analysis of efficacy endpoint.

Per protocol analysis set: a subset of efficacy analysis set of patients without any importance protocol violation, as defined by the sponsor prior to the data base locked (adhere to ICH E3 guidance) Important protocol deviations are a subset of protocol deviations that might significantly affect the completeness, accuracy, and/or reliability of the study data or that might significantly affect a subject's rights, safety, or well-being. For example, important protocol deviations might include enrolling subjects in violation of key eligibility criteria designed to ensure a specific subject population or failing to collect data necessary to interpret primary endpoints, as this may compromise the scientific value of the trial.

# 4. Statistical Analysis

# 4.1 General Considerations for Statistical Analysis

#### 4.1.1 General Rules

No statistical hypothesis testing or inferential analyses are planned. The general analytical approach for all endpoints will be descriptive in nature.

Continuous variables (such as age) will be summarized with the observed number, mean, median, standard deviation, minimum, and maximum; categorical variables will be summarized with frequency and percentage of each category.

Unless otherwise specified, in summary tables of continuous variables, the minimum and maximum values will be displayed to the same number of decimal places as the raw data; the mean, median, and percentiles will be presented to 1 extra decimal place compared to the raw data; and the standard deviation will be displayed to 2 extra decimal places compared to the raw data. The maximum number of decimal places is 3

and values will be truncated to 3 decimal places in situations where there are more than 3 decimal places. Frequency tabulations will be presented by number and percentage, where the percentage is presented in parenthesis to 1 decimal place.

# 4.1.2 Baseline Definition and Change from Baseline and Percent Change from Baseline

Baseline data are defined as last non-missing assessment which are collected prior to or on the day of first dose, and must be prior to the administration of first dose, including scheduled and unscheduled visits, unless otherwise specified. Hence, change from baseline = post-baseline value – baseline value. Percent change from baseline = (post-baseline value – baseline value)/ baseline value×100%.

#### 4.1.3 Study Day

If the date of assessment occurs on or after the first dose date, then study day will be calculated as (date of assessment - date of first dose) + 1. If the date of assessment occurs prior to the first dose date, then study day will be calculated as date of assessment - date of first dose. There is no study day 0.

#### 4.1.4 Visit Window

The nominal visit as defined in protocol and recorded on the Case Report Form (CRF) will be used in the statistical analyses unless other specified. Regarding efficacy endpoints, the analysis visit during follow-up period will be dynamically derived. For instance, if the subject finished the last dosing visit at Week 14, the first follow-up visit (i.e. FU1) will be set as the first visit after Week 14 (i.e. Week16) and subsequent follow-up visits will be derived accordingly as Week18, Week20, Week 22, Week24, and Week 26. Unscheduled data will not be windowed into planned analysis visits for summary tables but will be included in overall post-baseline summaries, such as worst or last values.

In addition, unscheduled data will be listed and may be plotted in figures based on study days.

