AD = atopic dermatitis; AE = adverse event; ALT = alanine aminotransferase; aPTT = activated partial thromboplastin time; AST = aspartate aminotransferase; CCL-17 = C-C chemokine ligand 17; D = day; EASI = Eczema and Severity Index; ECG = electrocardiography; GGT = gamma glutamyl transferase; HbsAg = hepatitis B surface antigen; HBV = hepatitis B virus; HCV = hepatitis C virus; HIV = human immunodeficiency virus; ICF = Informed Consent Form; IGA = Investigator's Global Assessment; IgE = immunoglobulin E; IL = interleukin; INR = international normalized ratio; LDH = lactate dehydrogenase; PD = pharmacodynamic; PH-2 = Patient Health Questionnaire-2; PK = pharmacokinetic; PP-NRS = Peak Pruritus Numerical Rating Scale; PT = prothrombin time; Q2W = every 2 weeks; QW = every week; RBC = red blood cell; SC = subcutaneous; TARC = thymus and activation regulated chemokine; W = week; WBC = white blood cell.

- 1. Screening duration varies by prior AD treatment and the Investigator should consult Section 7.2 for required washout duration. For patients not requiring washout, screening assessments should be conducted after ICF been signed and the screening period will take up to 2 weeks; once they complete their screening assessments and meet all study inclusions/exclusions, the patients will advance directly to W1D1. For patients requiring washout, screening assessments should be conducted after ICF been signed, if all inclusion/exclusions are met, they will be notified by the study sites to start the washout for prior AD treatment. Screening assessments should be repeated if they are performed ≥14 days before W1D1.
- 2. W1D1 pre-dosing is set to confirm the eligibility of patients.
- 3. BSI-045B administration after W4 (4 loading doses) at Q2W interval to Week 24.

V4.0_8 Jul 2024 Page 18 of 68

- 4. Order of assessments: When collecting PK, immunogenicity, biomarker, and clinical laboratory samples, vital signs, and/or ECG assessments are scheduled to occur at the same time point, ECG and vital signs testing will be performed prior to blood collections. The preferred order of assessments is: 1) ECG, 2) vital signs, 3) PK, immunogenicity, and biomarker sampling, 4) clinical laboratory sampling.
- 5. Height and weight, and BSA affected by AD should be determined at the Screening physical examination. BSA affected by AD should also be determined at W1D1 pre-dosing. Symptom-driven examinations will be performed at other time points beyond screening.

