- 12. PK blood sample collection: Within 1 h before each dose during the Treatment Period.
- 13. Immunogenicity blood sampling: Blood samples are to be collected at W1D1, W2, W3, W4, W8, W12, W16, W20, and W24 within 1 h before each dose during the Treatment Period.
- 14. Biomarker blood sample collection: Assessments are TARC/CCL-17, periostin, and IgE. Samples are to be obtained at W1D1, W2, W3, W4, W8, W12, W16, W20, and W24 within 1 h before each dose during the Treatment Period.

V4.0_8 Jul 2024 Page 19 of 68

Table 2. Follow-up, End of Study, and Early Withdrawal

	Follow-up Period						
Study Procedure	FU1 (2 weeks after last dose±3d)	FU2 (4 weeks after last dose±3d)	FU3 (6 weeks after last dose±3d)	FU4 (8 weeks after last dose±3d)	FU5 (10 weeks after last dose±3d)	FU6 (12 weeks after last dose±3d)	(+7d)
12-lead ECG ²	X						X
Vital signs ²	X	X	X	X	X	X	X
Physical examination (system driven)		X		X		X	X
Clinical labs ^{2,3}		X		X		X	X
Blood pregnancy test (females of childbearing potential only)							X
Urine pregnancy testing (females of childbearing potential only)		X		X		X	
Efficacy assessments and patient diary (EASI, IGA, facial IGA, PP-NRS) ⁴	X	X	X	X	X	X	X
PK sample collection ^{2,5}	X	X	X	X	X	X	X
Immunogenicity sample collection ^{2,6}		X		X		X	X
PD Biomarker sample collection ^{2,7}		X		X		X	X
Assess concomitant medications	X						
Monitor and document AEs							

AE = adverse event; ALT = alanine aminotransferase; aPTT = activated partial thromboplastin time; AST = aspartate aminotransferase; CCL-17 = C-C chemokine ligand 17; EASI = Eczema and Severity Index; ECG = electrocardiography; GGT = gamma glutamyl transferase; IGA = Investigator's Global Assessment; IgE = immunoglobulin E; IL = interleukin; INR = international normalized ratio; LDH = lactate dehydrogenase; PD = pharmacodynamic; PK = pharmacokinetic; PP-NRS = Peak Pruritus Numerical Rating Scale; PT = prothrombin time; RBC = red blood cell; TARC = thymus and activation regulated chemokine; W = week; WBC = white blood cell

- 1. Early withdrawal: Early withdrawal assessments must be completed within 7 days after the last treatment with BSI-045B or within 7 days after the patient's decision to discontinue study treatment, whichever occurs first. When medically feasible, the Medical Monitor should be consulted prior to study drug discontinuation.

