7.1 Study Dosing

The total number of evaluable patients with AD will be approximately 20 to 24.

Patients will initially be treated with a loading dose of BSI-045B given QW for 4 weeks. Thereafter, BSI-045B will be given at Q2W interval to Week 24.

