# 2. Project Overview

#### 2.1 Study Design

The study design is presented in the Schema. The study is a multicenter clinical trial and is designed as a proof-of-concept study to evaluate the efficacy, safety, tolerability, PK, immunogenicity, and PD of BSI-045B following SC injections.

The present study, which is intended to assess the efficacy and safety of BSI-045B in moderate to severe AD patients, is being conducted as a proof-of-concept study prior to performing a more traditional Phase 2 trial. If this study is successful, the Sponsor plans to conduct a future Phase 2b, randomized, blinded, dose-finding trial that will formally compare BSI-045B with placebo and/or other treatments for AD.

The study will enroll patients with moderate to severe AD. Eligible patients will receive BSI-045B 300 mg treatment, firstly at every week (QW) during Week 1 to Week 4, and then every 2 weeks (Q2W) to Week 24.

Patients will start with a washout period for anti-AD treatment prior to study treatment, including systemic and topical agents and phototherapy. The duration of the washout period varies by therapy and the Investigator should consult section 7.2 in the protocol. Eligible patients who complete the washout period for previous therapies for AD will be treated with BSI-045B as described above.

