#### 4.7.1 Eczema Area and Severity Index (EASI)

The EASI score is a composite index that measures the severity of AD based on the average intensity of four clinical signs (erythema, edema/papulation, excoriations, and lichenification) at four body areas (head, neck, upper extremities, and trunk and lower extremities), and the percentage of affected area for each of the four body areas.

The baseline for EASI is defined as the score measured prior to dosing on Day 1.

Measured values, changes from baseline and percent change from baseline in EASI score will be summarized descriptively on scheduled visit.

The primary efficacy endpoint is the proportion of subjects with EASI75 (a 75% reduction in the EASI score) at 2 weeks after last dose at Week 24. The exploratory endpoints include the proportion of subjects achieving EASI90 at Weeks 26 (2 weeks after last dose at Week 24), the proportion of patients with EASI50 at Week 26 (2 weeks after last dose at Week 24). The corresponding 95% two-sided confidence intervals (CIs) will be calculated using the exact binomial distribution and presented for EASI75, EASI90, and EASI50.

For primary analysis, the percent change from baseline in EASI score, EASI50, EASI75, EASI90 in the EASI score will be calculated with observed data. If the subject has missing value for EASI at scheduled visit, the subject will be excluded from the calculation of proportion at specify visit.

Mean (±standard deviation) of the percent change from baseline in EASI score with observed data will be plotted at scheduled visit.

For sensitivity analysis, the missing value will also be imputed with last observation carried forward (LOCF) method. The imputed data for the percent change from baseline in EASI score will be summarized descriptively on scheduled visit. The proportion of subjects with EASI50, EASI75 and EASI90 at 2 weeks after last dose at Week 26 will also be calculated with imputed data.

A listing of all EASI score will be provided by subject number.

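### Read literally, the follow-up visit rule in SAP 4.1.4 labels efficacy scores 1 to 3 weeks early for patients whose last dose is at W1, W2 or W3; only exploratory by-visit outputs are affected

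*SAP*

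**What the plan says.** SAP 4.1.4 uses nominal visits in general but makes an exception: "Regarding efficacy endpoints, the analysis visit during follow-up period will be dynamically derived". The rule is then given by one example, a patient whose last dosing visit is Week 14. For that patient "the first follow-up visit (i.e. FU1) will be set as the first visit after Week 14 (i.e. Week16". FU2 to FU6 then take the next five labels on the visit list in turn, ending at Week 26.

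Protocol Table 2 ties follow-up to the last dose: "FU1 (2 weeks after last dose±3d", then every two weeks to FU6 at 12 weeks.

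Treatment visits are not evenly spaced. SAP 2.1 has dosing "firstly at every week (QW) during Week 1 to Week 4, and then every 2 weeks (Q2W) to Week 24", and Protocol Table 1 (note 3) agrees: "BSI-045B administration after W4 (4 loading doses) at Q2W interval to Week 24". The SAP has no separate labelling rule for a stop in the weekly phase.

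The labels are used in SAP 4.7.1, where "percent change from baseline in EASI score will be summarized descriptively on scheduled visit", first with observed data (also plotted) and again with LOCF. SAP 4.7.3 plots percent change in PP-NRS by scheduled visit.

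**The concern.** The example works because at Week 14 the treatment and follow-up visits are both two weeks apart. In the weekly phase they are not: moving one place along the visit list is one week, while moving one place along the follow-up schedule is two.

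Patients who stop that early can still reach the tables. Protocol 7.11 expects further follow-up after treatment is stopped. Protocol 7.3 replaces patients who have not completed five doses, but SAP section 3 keeps anyone with one dose and one post-baseline efficacy assessment in the Efficacy Analysis Set. At stake is whether the by-visit EASI curve, a listed exploratory endpoint, and the PP-NRS plot show these patients at the right time.

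**Working it through.** **Inputs**
- Visit list (Protocol Table 1, plus Week 26): W1, W2, W3, W4, W6, W8, ..., W24, W26.
- FUk takes place 2k weeks after the last dose, k = 1 to 6, ±3 days (Protocol Table 2).
- Windows: ±1 day at W2 and W3, ±3 days from W4 (Protocol Table 1). Nominal day of week w, counted from first dose: 7(w − 1) + 1.

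**Formulas**, for a last dose at week s
- Actual week of FUk = s + 2k.
- Label under the literal rule = the k-th entry after Ws in the visit list.
- Error = actual week − label.

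**The SAP's own example.** For s = 14, actual weeks are 16, 18, 20, 22, 24, 26 and the labels are the same. The error is 0 at all six visits, so the example reproduces.

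**Other stopping points**

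| Last dose | Actual weeks, FU1 to FU6 | Labels | Weeks too early |
|---|---|---|---|
| W1 | 3, 5, 7, 9, 11, 13 | W2, W3, W4, W6, W8, W10 | 1, 2, 3, 3, 3, 3 |
| W2 | 4, 6, 8, 10, 12, 14 | W3, W4, W6, W8, W10, W12 | 1, 2, 2, 2, 2, 2 |
| W3 | 5, 7, 9, 11, 13, 15 | W4, W6, W8, W10, W12, W14 | 1, 1, 1, 1, 1, 1 |
| W4 | 6, 8, 10, 12, 14, 16 | W6, W8, W10, W12, W14, W16 | 0 throughout |

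**Do the visit windows absorb the error?** Take the earliest permitted FU1 against the last day of the window of its label.
- W1 stop: Day 1 + 14 − 3 = Day 12; the W2 window ends on Day 8 + 1 = Day 9. No.
- W2 stop: Day 8 − 1 + 14 − 3 = Day 18; the W3 window ends on Day 15 + 1 = Day 16. No.
- W3 stop: Day 15 − 1 + 14 − 3 = Day 25; the W4 window ends on Day 22 + 3 = Day 25. The two meet only in this extreme case.

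**The alternative reading (last dose plus two weeks per follow-up).** The actual weeks above then become the labels. All six W2-stop visits fall on scheduled weeks. W1-stop FU2 to FU6 (weeks 5, 7, 9, 11, 13) and all W3-stop visits (weeks 5 to 15, odd) fall on weeks with no scheduled visit.

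**Would a nearest-visit rule do?** Not for those odd weeks. Week 5 is one week from both W4 and W6, and the others are ties in the same way. Resolving ties to the earlier visit gives a W3 stop exactly the labels in the table; resolving them to the later visit makes each label one week late.

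**Does any of this reach Week 26?** The highest labels in the three affected rows are W10, W12 and W14. The observed-data EASI75 at Week 26 excludes these patients as missing (SAP 4.7.1). The LOCF value at Week 26 is their last observation, whatever its label.

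**The case against.** The strongest objection is that the rule is only illustrated, not stated in general. The two-weeks-per-follow-up reading fits the Week 14 example equally well, agrees with Protocol Table 2 and removes the shift. A reader might infer from the table that scores will certainly be misplaced; the documents do not support that much. They support a narrower statement: the literal wording gives the wrong week in the weekly phase, and the alternative leaves many visits without a label. Either way the SAP does not settle these visits.

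A reader might also infer that the primary result is biased. It is not, because no affected visit can carry a Week 26 label. Nor is a by-visit effect shown for IGA or facial IGA: SAP 4.7.2 and 4.7.4 specify their response only at two weeks after the Week 24 dose.

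A third inference is that mislabelling causes off-drug scores to be averaged with on-treatment scores. That mixing comes from keeping early stoppers in the by-visit summaries, and correct labels would not end it. For the same reason, the shift in a visit mean from including rather than omitting one such patient does not measure the labelling error. Where the patient stays at the same visit, the labelling error is that patient's own change over one to three weeks divided by the number of patients at the visit. The documents give nothing from which to estimate it.

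Finally, the affected group may be empty. It requires a stop after one to three of 14 doses and continued attendance. A patient who leaves the study altogether owes only a safety examination, and only with consent (Protocol 7.12). The analysis is descriptive, with no hypothesis testing (SAP 4.1.1).

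**Conclusion.** The point stands as a small correction. On its literal wording, SAP 4.1.4 places follow-up scores up to 3 weeks early after a last dose at W1, up to 2 weeks early after W2, and 1 week early after W3. From W4 on it is right. The outputs concerned are the by-visit EASI change summaries (observed and LOCF), the observed-data EASI plot and the by-visit PP-NRS plot. Any by-visit EASI50/75/90 percentages produced under Protocol 7.9.3 would inherit the same labels.

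This rests on the literal reading, on nominal visit days counted from first dose, and on at least one patient stopping within the first three doses and attending follow-up. The documents give no such count. The effect on any visit mean cannot be sized from the documents.

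**What to change.** In SAP 4.1.4, derive the follow-up analysis week from study day (weeks since first dose; study day is already defined in SAP 4.1.3). Use a scheduled-visit label only when the assessment falls inside that visit's protocol window. List follow-up scores at weeks with no scheduled visit (5, 7, 9, 11, 13, 15), or plot them by study day, instead of forcing them to a neighbouring visit. State that the rule covers EASI and PP-NRS.

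Three clarifications keep the change contained:
- FU1 after the Week 24 dose remains Week 26, as the endpoint is defined.
- LOCF carries forward the last score by date, including off-schedule scores, so the Week 26 LOCF value does not change.
- The rule may be restricted to last doses before W4. After later stops the present labels are already right, and a strict window could drop a visit that has drifted: a dose 3 days late plus a follow-up 3 days late is 3 + 3 = 6 days, outside ±3.

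The cost is a short SAP amendment and a derivation change, with no new data. The downside is that a few off-schedule scores from very early stoppers leave the by-visit tables and appear only in listings or study-day plots.

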#### 4.1.5 Missing Data

Unless otherwise specified, missing data will be treated as missing, ie, no special handling will be performed. For demographic and baseline characteristics, each variable will be analyzed and/or summarized using the available data. Details of efficacy and safety data handling will be documented in efficacy and safety analyses section.

# 4.1.6 Partial/Missing Dates

For partial dates, the algorithms for imputation will vary depending upon the parameter; missing or incomplete medications start and stop dates will be imputed to determine

whether the medications are taking concomitantly. Missing AE start dates will be imputed to determine whether the adverse events are treatment emergent. In listings, all dates will be listed as recorded. The details of imputation rules can be found in Appendix 1.

#### 4.2 Disposition of Subjects

The number and percentage of subjects in the following disposition categories will be summarized:

- Subjects signed the informed consent
- Subjects screen failure and reason for screen failure
- Subjects enrolled
- Subjects received study drug
- Subjects completed/discontinued treatment and reason for discontinuation
- Subjects completed/discontinued study and reason for discontinuation

The number and percentage of subjects in each analysis set and reasons for exclusion from an analysis set will be summarized in all subjects.

A listing of subject disposition based on all subjects will be provided.

#### 4.3 Protocol Deviations

A protocol deviation is defined as any change, divergence, or departure from the study design or procedures defined in the protocol.

An important protocol deviation is defined as a protocol deviation that might significantly affect the completeness, accuracy, and/or reliability of the study data or that might significantly affect a subject's rights, safety, or well-being.

A summary of the number and percentage of subjects with important protocol deviations by type of deviation will be provided in safety analysis set.

A listing of all protocol deviations will be provided by subject number.

#### 4.4 Demographics and Baseline Information

Demographics and baseline information analysis will be summarized in safety analysis set.

# 4.4.1 Demographics

Descriptive statistics will be performed for demographic variables. The following information will be tabulated and summarized.

 Age (years) = Integer of [(Date of Signature of the Informed Consent - Date of Birth + 1)/365.25].

• Gender: Male and Female

- Race: White, American Indian or Alaska Native, Black or African American, Asian, Native Hawaiian or Other Pacific Islander, and Other
- Height (cm)
- Body Weight (kg)
- Body Mass Index (BMI)  $(kg/m^2)$  = weight (kg)/height  $(m)^2$
- Smoking History: Current, Former, Never
- Alcohol History: Current, Former, Never

The demographics list will be provided subject number.

#### 4.4.2 Drug Abuse, Donation History and Allergy History

Drug abuse, donation history and allergy history will be listed by subject number.

#### 4.4.3 Assessment of Suicidality (PH-2)

Assessment of suicidality (PH-2) will be listed subject number.

